### Equipment

- Each Audiologist will be asked to provide a standard calibrated audiometer and a tympanometer.
- Stage A calibration checks will be carried out on testing equipment as per standard national practice
- Data capture form (Appendix 15)
- Sticker to mark completion of station, to be inserted in child's route map

### Personnel

The local Audiologist, Audiological Physician or ENT surgeon.

## OUTCOME MEASURES FROM RESEARCH AUDIT CLINIC AND CLINICAL RECORDS

---

- Record Audiological/otological interventions carried out
  - Grommets
  - Hearing aid use past/current

- Management of middle ear effusion to include watchful waiting
- Other medical/Otological procedures
- Audiological/ontological assessment in 5-year-olds
  - Full audiogram testing AC and BC as appropriate to assess hearing thresholds rather than using screening audiometry
  - Type of hearing loss
  - Degree of hearing loss
  - Management of hearing loss as recorded on the audit assessment day
  - Middle ear function assessed by tympanometry

## ASSESSMENT OF DENTAL ARCH RELATIONSHIP

---

### Method

1. The cleft team orthodontist (or appropriately trained dentist/dental care professional) will complete the presurgical orthopaedic treatment form and will take an alginate impression together with a wax squash-bite in centric occlusion. The overjet will also be recorded. If impressions cannot be obtained then intra oral photographs of the teeth in occlusion will be obtained.
  - a. Intra-oral photographs should include a frontal view, right and left lateral views and, if possible, a palatal view.
  - b. The orthodontist (or appropriately trained dentist/dental care professional) should ensure that the patient is in the correct occlusion when taking the photographs.
  - c. The orthodontist (or appropriately trained dentist/dental care professional) should check that the photographs are adequate to assess crossbites and incisor inclination prior to allowing the patient to leave
  - d. A clinically recorded overjet measurement for each anterior tooth should be taken at that same appointment and should be provided with the photographs'

The research team will either

- a. receive a copy of the trimmed models made from the impressions
- b. take the impressions with them to make a trimmed model for the research team and a copy model for the cleft centre

- c. The research team will need to receive a copy of the photographs when these have been taken in place of the models.
2. The model will be placed in model box for transportation or the impressions will be placed in labelled plastic bags with lab cards and transported by the research team in a “cool bag” to the laboratory.
3. At the laboratory, the impressions will be cast and models will be prepared by an orthodontic technician in the laboratory according to an established protocol and the bases will be labelled with the participants ID number. For those cleft centres that provided an impression a duplicate set of trimmed models will be sent to them. If models are provided by the cleft centres then these will be duplicated so that all casts and models will be in a standard format when evaluated as an outcome measure.

#### Equipment

- Presurgical orthopaedic treatment form (Appendix 16)
- Sets of small trays suitable for use in five-year olds
- Wax for squash bites
- Cool box to transport the impressions, plastic bags, identification labels
- Alginate impression material, fixative & disinfectant
- Mixing bowls and spatulas
- Sticker to mark completion of station, to be inserted in child’s route map
- If appropriate an alginate impression of the child’s finger may be taken and cast in plaster as a small memento of the child’s visit.

### Personnel

The impressions will be taken by the orthodontist (or appropriately trained dentist/dental care professional)

A local dental surgery assistant to mix the alginate

Orthodontic technician (will be located in the North Bristol laboratory)

### OUTCOME MEASURES FROM RESEARCH AUDIT CLINIC AND CLINICAL RECORDS

- Inter-arch relationships measured with the 5 year old index and potentially the 4 scale index developed in Manchester.

## ASSESSMENT OF DENTAL HEALTH

---

### Methods

1. The paediatric dentist and/or therapist will examine the clinical records and record information on the data capture form.
2. The paediatric dentist and/or therapist will ask the parent about the following;
  - a. Who provides their regular dental care
  - b. Have they been assessed by a Consultant in Paediatric Dentistry?
  - c. Has their child ever had a neonatal appliance? (show picture as example)
  - d. Has their child ever had nasoalveolar moulding? (show picture as example)
  - e. Details of functional problems with fistula if present
3. Using standard protocols and using data collection forms we will record the following:
  - a) dmfs for five year olds
  - b) Oral hygiene using the Index of Oral Cleanliness (21)
  - c) As part of the dental health assessment, the buccal occlusion will be recorded.

### Equipment

- Data capture form (Appendix 17)
- Dental mirrors
- Dental chair
- Dental light
- Forms to record buccal occlusion, dmfs and oral cleanliness
- Sticker to mark completion of station, to be inserted in child's route map

## Personnel

The Paediatric dentist or therapist will have received a standardised training and calibration for the CSAG II project.

## OUTCOME MEASURES FROM RESEARCH AUDIT CLINIC AND CLINICAL RECORDS

- Dentist providing usual care – general dental practitioner or specialist paediatric dentist
- Past dental treatment
- History of neonatal appliance
- Buccal occlusion, dmfs and oral cleanliness
- Presence/absence of a residual fistula

## ASSESSMENT OF SURGICAL DETAILS

---

### Method

The Cleft surgeon will examine the child and their clinical record and record information on the data capture forms. The examination will identify if any oral fistula is present and if there are any functional problems involved. The clinical record will provide information about phenotype and treatment.

### Equipment

- Data capture form (Appendix 18)

### Personnel

The Cleft surgeon.

## OUTCOME MEASURES FROM RESEARCH AUDIT CLINIC AND CLINICAL RECORDS

---

- Type of primary lip repair
- Surgical complications
- Type of palate repair
- Presence of oral fistula

## 2-DIMENSIONAL ASSESSMENT OF FACIAL AESTHETICS

---

### Method

The assessment of facial aesthetics will follow the recommended guidelines for photography of cleft audit patients (22, 23). The child will be asked to sit on a chair placed 0.5 metres in front of a standardised black or white non-reflective background which has been mounted on a wall, or a plain wall can be used as background. The hair will be arranged to show the entire ear.

The following views will be taken for each child with the lens length fixed to give standardised magnification.

1. Left lateral face (1:8)
2. Right lateral face (1:8)
3.  $\frac{3}{4}$  left lateral face (1:8)
4.  $\frac{3}{4}$  right lateral face (1:8)
5. Facial (1:8)
6. Facial smiling (1:4)
7. Whistling (1:4)
8. Worm's eye view (1:4)
9. Lip & Nose (1:3)

Each photograph will be catalogued and recorded for each patient

### Equipment

- Camera Nikon D3s or other appropriate camera
- 105mm macro lens
- Lighting equipment for camera

- Black or white background paper/sheet or plain wall
- Black tack
- Sticker to mark completion of station, to be inserted in child's route map
- Capture form (Appendix 19)

#### Personnel

The photographs will be taken by the cleft centre medical photography personnel.

#### OUTCOME MEASURES FROM RESEARCH AUDIT CLINIC AND CLINICAL RECORDS

- Profile and frontal photographs to determine the appearance of the lip, nose and profile of 5-year-olds using the Five Point Scale (24)

## ASSESSMENT OF HEIGHT, WEIGHT AND HEAD CIRCUMFERENCE

---

### Method

#### **Height**

Position - Remove shoes, stand the young person with feet flat, so that underside of heels are in contact with the ground. The heels are placed together, so that the medial malleoli are touching, (unless the child has knock knees). The child stands straight so that heels, calves, buttocks and shoulders are in contact with the vertical backboard of the stadiometer. Shoulders should be relaxed and sloping forward in a natural position, hands and arms are loose and relaxed with palms facing medially. The head is positioned in the Frankfurt plane\*.[\*Frankfurt plane - the lower orbit of the eye in the same plane as the upper margin of the external auditory meatus.]

Measuring - Slide the headboard down the backboard until it touches the young person's head. To ensure that the head stays in contact with the headboard and to minimise the effect of hair thickness, place a 1kg weight on the headboard. Ask the young person to "relax the shoulders and stretch up but keep the heels on the ground". Assist this stretching by applying gentle upwards pressure beneath the mastoid processes. Check that the heels are touching the ground. Read the height from the counter to the last completed millimetre and record on the data sheet

#### **Weight**

Ask the young person if they have passed urine before coming to the measuring session. Record on the data sheet. Enter either MALE or FEMALE STANDARD for the young person depending on the gender, then enter the young person's height in centimetres to the nearest centimeter (up to point 4 is rounded down and point 5 and above is rounded up). The young

person, undressed to underwear / lightweight sports clothes, then steps on to the measuring platform, which has been wiped with disinfecting alcohol. Position young person in such a manner, that both feet are located in parallel with the toe and heel in contact with their respective electrodes. Encourage the young person to stand still, front facing without bending the knees.

Measuring - Measurement has been completed when the weight and fat ratio reading are fixed and the buzzer beeps. Ask the young person to step off the measuring platform. Remove the printout from the printer, and clip it to the data sheet. Record the young person's weight, impedance, fat percentage and TBW on the data sheet.

### **Head Circumference**

Position with the young person sat comfortably and relaxed with head in the Frankfurt plane.

Measuring - The head is measured at the widest horizontal circumference above the eyebrows and ears; the tape is kept taut but not tight.

### Equipment

- Harpenden Stadiometer
- Harpenden anthropometric tape
- Tanita scales
- Height, Weight and Head circumferences report form (Appendix 20)

### Personnel

The research staff together with cleft nurse/clinic nurse

## OUTCOME MEASURES FROM RESEARCH AUDIT CLINIC AND CLINICAL RECORDS

- Height
- Weight
- Head Circumference

## ASSESSMENT OF PSYCHOSOCIAL STATUS

---

### Method

The parents/guardians of all children will be able to complete the psychology questionnaire that addresses psychosocial status. This will be achieved in one of the following ways;

1. A cleft team psychologist or a member of the research team will administer the questionnaire to the parent.
  - a. Self completion
  - b. Psychologist assists with the questionnaire
2. The psychology questionnaire will be sent home beforehand, at the clinic the psychologist will collect the questionnaire and address any aspects if needed.

### Equipment

- Copies of the psychology questionnaire (Appendix 21)
- Biro
- Envelopes

### Personnel

Local cleft team psychologist or research team member experienced in counselling

## OUTCOME MEASURES FROM RESEARCH AUDIT CLINIC AND CLINICAL RECORDS

---

- Assessment of parental answers to the psychology questionnaire
  - Parent/guardian' perception of the impact of the cleft for their child.
  - Parent/guardian' perception about their child's appearance.

## ASSESSMENT OF SATISFACTION OF SERVICE

---

### Method

The parents/guardians of all children will be given the questionnaire “satisfaction of service” together with a free post labelled envelope at the end of the research audit clinic day. They will be asked to complete the questionnaire, either to return it to the questionnaire box or mail it back to the researchers within a week. If it is not returned within 7-14 days, the research team will mail out questionnaire together with a free post labelled envelope asking them to complete the questionnaire.

### Equipment

- Copies of the satisfaction of service questionnaire (Appendix 22)
- Biro
- Free post labelled envelopes

### Personnel

Research team member

## OUTCOME MEASURES FROM RESEARCH AUDIT CLINIC AND CLINICAL RECORDS

---

- Assessment of parental answers to the satisfaction of service questionnaire.

## HEALTH & LIFESTYLE QUESTIONNAIRE

---

### Method

The parents/guardians of all children will be asked at the end of the research audit clinic day if they would like to take home and complete a health and lifestyle questionnaire. If they agree, they will be given the “health and lifestyle questionnaire” together with an information sheet and a free post labelled envelope. They will be asked to complete the questionnaire and mail it back to the researchers within a week. If it is not returned within 7-14 days, the research team will mail out questionnaire together with a free post labelled envelope asking them to complete the questionnaire. The questionnaire focuses on a variety of psychosocial aspects (25-28) and personal costs concerned with caring for a child with a cleft lip and / or palate.

### Equipment

- Health and Lifestyle questionnaire (Appendix 23).
- Separate versions of the questionnaire will be provided for completion by the child’s mother and father and will be identified accordingly.
- Each questionnaire will be labelled with the child’s identification number.

### Personnel

The study team member who is running the data collection aspect of the audit clinic will be responsible for administering this questionnaire.

## OUTCOME MEASURES FROM RESEARCH AUDIT CLINIC AND CLINICAL RECORDS

---

The questionnaire comprises several parts measuring different aspects of family life and caring for a child, and personal costs incurred by the parent/guardian as result of caring for their child with UCLP. These are as follows:

- A basic demographic section collecting data about:
  - Ethnic group
  - Parent/guardian' age when the child was born
  - Parent/guardian' highest level of education
  - Parent/guardian' current / most recent occupation
  - Family set-up: who lives at home and their relationship to the child
  - Details of other family members with cleft lip / palate ad relationship to the child
- The parent-child relationship
  - Warmth
  - Support
  - Control
- A stress inventory (measuring stress over the previous week)
- A measure of parental protectiveness towards the child
- The General Health Questionnaire
  - Physical and mental health
  - General well-being
- A measure of child temperament
- A measure of child vulnerability
- An estimation of personal direct costs and indirect costs

## **STATISTICAL ANALYSIS**

---

We will use multiple linear regression, logistic regression and ordered logistic regression where appropriate to compare the outcomes with those observed in 1998 and to control for confounding factors; this will enable evaluation of the impact of centralisation on outcome of treatment for CLP. We will use multi-level models to explore variations in current practice (including areas such as skin closure techniques, antibiotic use and speech and language therapy) and outcomes across centres.

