## **BACKGROUND**

---

Cleft lip and palate (CLP) is one of the most common congenital abnormalities in the UK with an estimated prevalence of 1 in 700 live births (1, 2). Prevalence varies by ethnicity, geographic origin and gender with males more likely than females to have a unilateral cleft lip and palate (UCLP)(3). In addition a left-sided cleft is more common than a right sided cleft (4). Care of a person with cleft lip and palate is complex. It usually begins with antenatal diagnosis and continues into adulthood. Treatment of cleft lip and palate is resource intensive requiring evaluation and care from a range of specialists including Audiologists, Cleft Nurse Specialists, Clinical Geneticists, Clinical Psychologists, Dieticians, Orthodontists, Medical Photographers, Paediatricians, Paediatric Dentists, Restorative Dentists, Speech and Language Therapists, and Surgeons (from ENT, Plastic Surgery, and Maxillofacial Surgery) to achieve the optimum outcome.

In the 1990s concerns were expressed over the standard of care and outcome in children with cleft lip and palate in the United Kingdom (UK) and the training of those health care professionals providing it (5-8). These concerns led the Clinical Standards Advisory Group (CSAG), to commission a national survey of the care and outcome in children with CLP – referred to in this document as the CSAG survey (9, 10). This survey began in 1996 and ran over a 15 month period. The survey aimed to include all non-syndromic children in the U.K., born with a complete UCLP aged either 5 or 12-years of age. The outcomes assessed included the quality of speech, hearing, naso-labial appearance, dental arch relationships, oral health, the success of alveolar bone grafts (in the 12 year old cohort only) and child/parent satisfaction (11-14).

In 1998 the group published their main report (1). Fifty seven centres were identified as providing a cleft service in the U.K. with the number of cases being treated per year varying considerably. They found that the outcomes of cleft care in the U.K. were generally poor. One of the key findings was the poor outcome with respect to dental arch relationships and profile, when compared with three European centres (Oslo, Bergen, and Nantes). It was reported that 36% of 5 year olds and 39% of 12 year olds with UCLP had a poor dental arch relationship. Other centres in Europe have shown outcomes with less than 10% of UCLP cases having poor dental arch relations (1).

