On the basis of this survey it was concluded that some children with CLP were not receiving optimal care in the UK. The group made nine recommendations to the government all of which were accepted (Appendix 1). The acceptance of these recommendations led to a major reorganization of cleft services across the UK, with the concentration of resources and expertise in fewer units. Current arrangements have configured eleven cleft centres carrying out operations at seventeen cleft sites in the UK working within multi-disciplinary teams.

The overall aim of the current study is to evaluate the impact of this service reorganization on the standard of care currently provided for, and the outcomes achieved in, children with cleft lip and palate in the UK. Centralisation of care in a smaller number of larger centres has important resource and logistic implications for both users and service providers and this study will attempt to estimate the cost and cost effectiveness of the changes in cleft care. The work is funded by a NIHR grant "Evidence based health care for major congenital and acquired problems of the head and neck", Reference Number: RP-PG-0707-10034.

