### **STUDY SAMPLE**

---

We aim to study all 5-year-old children from cleft centres in the UK born in the two year period between **01/04/2005 to 31/03/2007**. At the time of the audit the child should be aged between 5 years 3 months and 5 years 9 months. The original CSAG survey identified 326 five-year-olds born with UCLP in the UK over a two year period and outcome records were collected

for 239 five-year-olds (1). This represents a recruitment rate of 73%. As care is now centralised and better documented we anticipate that we will be able to obtain information from at least 250 patients born with with UCLP.

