## **POWER CALCULATIONS**

---

In the baseline survey of outcomes in five year old children with CLP nearly 40% had poor dental arch relations; 40% had untreated dental caries and 19% were judged to be impossible to understand or were just intelligible to strangers. With a sample size of 250 children and setting the (2-sided) value of alpha at 0.05 we will have over 90% power to detect an absolute difference in dental arch relations and caries of 20% and over 80% power to detect an absolute difference in intelligible speech of 10%.

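### The regressions named for the comparison with the original CSAG survey, and the power statement, make no allowance for clustering of children within cleft centres

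*Protocol*

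**What the plan says.** The Protocol's Statistical Analysis section assigns methods to two tasks. For the comparison between surveys: "We will use multiple linear regression, logistic regression and ordered logistic regression where appropriate to compare the outcomes with those observed in 1998". The same sentence adds control for confounding and says that this will allow the effect of centralisation on outcome to be evaluated. For the second task: "We will use multi-level models to explore variations in current practice", together with variation in outcomes across centres. No centre term or clustered variance is mentioned for the first task.

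Power Calculations starts from "With a sample size of 250 children", "setting the (2-sided) value of alpha at 0.05". It claims over 90% power for 20-point differences in dental arch relations and caries, and "over 80% power to detect an absolute difference in intelligible speech of 10" percentage points. It mentions no ICC, design effect or centre.

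Background describes the grouping. At the time of the original survey: "Fifty seven centres were identified as providing a cleft service in the U.K". Now: "eleven cleft centres carrying out operations at seventeen cleft sites in the UK". The Rationale for the 5-year-old survey adds that centres centralised at different speeds and on different models of care.

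**The concern.** The authors expect practice and outcomes to vary by centre and plan a method that handles this, but name it only for the exploratory question. The between-survey comparison, which serves Objective 2, has the same clustered data. Its exposure is the organisation of the service, which acts at centre level, so between-centre variance enters the standard error of the contrast. Adjusting for child-level confounders does not in general remove it.

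Centralisation also makes the clusters larger, so the effect of clustering is greatest in the new cohort. At stake are the width of the intervals and the false-positive rate for the headline conclusion about a national reorganisation, and whether the stated speech power is reached.

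**Working it through.** **Inputs from the Protocol.** Current survey n2 = 250, two-sided alpha 0.05, baseline 40% for dental arch relations and caries, 19% for poor intelligibility (Power Calculations). Original survey n1 = 239 (Study Sample: "for 239 five-year-olds (1). This represents a recruitment rate of 73" per cent). Clusters: 57 centres then, 11 centres or 17 sites now (Background).

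**Assumptions.** The Protocol gives no ICC, so 0.01 to 0.10 is shown. Clusters are taken as equal in size. Mean cluster sizes are 239/57 = 4.2 then, and 250/11 = 22.7 or 250/17 = 14.7 now. The 4.2 is itself an assumption: the Protocol says 57 centres provided a service, not that 57 contributed to the 239 records.

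**Step 1: reproduce the stated power under independence.** Two-proportion test with pooled null variance, speech 19% to 9%:
- pooled p = (239 × 0.19 + 250 × 0.09)/489 = 0.1389
- null SE = √[0.1389 × 0.8611 × (1/239 + 1/250)] = 0.0313
- alternative SE = √[0.19 × 0.81/239 + 0.09 × 0.91/250] = 0.0312
- power = Φ[(0.10 − 1.96 × 0.0313)/0.0312] = Φ(1.24) = 89%

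The same calculation for 40% to 20% gives 99.8%. Both stated lower bounds are met.

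**Step 2: standard error and true error with clustering.** Design effect DE = 1 + (m − 1) × ICC in each survey. Under the null the common p cancels, so the true SE exceeds the independence SE by the factor √[(DE1/239 + DE2/250)/(1/239 + 1/250)]. The true two-sided error is 2 × [1 − Φ(1.96/factor)].

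Example, 11 centres, ICC 0.05: DE1 = 1.160, DE2 = 2.086; factor = √(0.01320/0.00818) = 1.27; 1.96/1.27 = 1.54; true error 12%.

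| ICC | Factor, 11 centres | True error | Factor, 17 sites | True error |
|---|---|---|---|---|
| 0.01 | 1.06 | 6% | 1.04 | 6% |
| 0.02 | 1.12 | 8% | 1.08 | 7% |
| 0.05 | 1.27 | 12% | 1.19 | 10% |
| 0.10 | 1.49 | 19% | 1.35 | 15% |

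Little depends on the old cluster size. With DE1 set to 1 (no clustering in the original survey), the 11-centre example gives √[(1/239 + 2.086/250)/(1/239 + 1/250)] = 1.24 and a true error of about 11%.

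**Step 3: power with clustering.** Multiply each survey's variance by its DE and repeat Step 1. The ranges for speech reflect pooling the null proportion on effective or on actual sample sizes. The dental column uses effective sizes, which gives the lower figure.

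| ICC | Speech, 11 centres | Speech, 17 sites | Dental and caries, 11 centres |
|---|---|---|---|
| 0.01 | 85-86% | 87% | 99.6% |
| 0.02 | 81-82% | 84-85% | 99% |
| 0.03 | 77-79% | 81-82% | 99% |
| 0.05 | 69-72% | 76-77% | 97% |
| 0.10 | 53-58% | 63-66% | 90% |

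**Step 4: where speech power falls below 80%.**

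| Null variance | 11 centres | 17 sites |
|---|---|---|
| Pooled on effective n | ICC 0.023 | ICC 0.034 |
| Pooled on actual n | ICC 0.027 | ICC 0.039 |
| Unpooled | ICC 0.033 | ICC 0.046 |

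**The case against.** Four arguments on the other side deserve weight.

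*Both surveys aim at every eligible child, and centres are not sampled.* For a purely descriptive then-versus-now contrast, conditional on the centres that existed, centre effects can be treated as fixed and between-centre variance need not enter the standard error. This stands for that target. It does not cover the use the Protocol makes of the comparison, which is to evaluate the effect of centralisation. That inference reaches beyond the particular centres.

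*The text names regression families and does not fix a variance estimator.* Logistic regression with clustered standard errors is still logistic regression, and a statistical analysis plan could specify it. This is possible. But the qualifier in the sentence most naturally governs which family suits which outcome, and the next sentence brings in multi-level models for a different purpose. Followed as written, the comparison ignores centre.

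*The stated power may be true.* A reader might infer that the speech power is overstated. The documents do not support that. The Protocol claims only more than 80%, independence gives about 89%, and the claim survives an ICC of 0.02 with either cluster count. Whether it fails depends on an ICC that the documents do not give, and the exact threshold shifts with the variance convention.

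*The old cluster size is not documented.* This is correct. It limits the precision of the figures but not their direction, since most of the inflation comes from the current survey.

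**Conclusion.** The concern holds for the analysis. The models named for the comparison with the original survey take no account of centre, and if outcomes vary between centres their standard errors are too small for an inference about centralisation. Under equal clusters and an ICC of 0.01 to 0.05, the true error of a nominal 5% test is about 6-12% with 11 centres or 6-10% with 17 sites.

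For power the supportable statement is narrower: the section makes no allowance for clustering, and the speech claim fails only above an ICC of about 0.02-0.03 (11 centres) or 0.03-0.05 (17 sites). It would also be wrong to infer that all the stated power is in doubt, because the dental arch and caries figures stay at or above 90% up to an ICC of 0.10. Unequal centre sizes, and the correction needed with so few clusters, would lower power somewhat below the figures shown.

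**What to change.** In Statistical Analysis, keep the same linear, logistic and ordered logistic families for the comparison with the original survey, and add a random intercept for centre within survey. Alternatively, use centre-clustered standard errors with a small-cluster correction. Say whether the cluster is the centre or the operating site. If centre codes cannot be obtained for the original data, apply the correction to the current cohort, where the design effect is largest.

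In Power Calculations, state an assumed ICC and the speech power that results: for example about 69-87% over an ICC of 0.01 to 0.05, spanning 11 centres and 17 sites under the two pooled-variance conventions.

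The cost is a sentence or two in each section, somewhat wider intervals and a less favourable stated power. No extra data are needed for the current survey, because the cleft centres themselves identify and schedule the children.
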